6. METHODS

6.1 INTERVENTION

Intervention occurs only in Phase 3 of the study. All data collection will occur in REDCap (Research Electronic Data Capture), a secure, HIPAA-compliant electronic data capture system hosted by the Research Informatics Core at Einstein (53). Survey collection will occur in the participant's browser. Daily diary collection will occur using an app (Status/Post) developed for this study to connect participants seamlessly to REDCap using an Apple device. Participants who do not have an Apple device will be provided with a study iPod. Interventions will be delivered through the Status/Post app.

Participants will be randomized to receive either the 1) CDST or 2) Headache Education version of the Status/Post App.

- 1) The Clinical Decision Support Tool (CDST) version of the Status/Post app will include several education modules with companion reminders. Education modules are individualized websites linked to the app that provide a consistent source of information about migraine management. Reminders are just-in-time notifications the participant receives in response to their adherence behaviors throughout the study that briefly remind participants about the education they received in response to their behaviors.

All participants will receive the Medication module, designed to provide information regarding appropriate use of acute and preventive migraine medication. Participants will be assigned to one of three behavioral management education module based on their individual adherence to that behavioral management strategy during the Phase 2 of the study. The three behavioral management education modules are: Stress Management, Sleep Management, and Consistent Eating/Hydration. Each is designed to provide education about why the behavioral strategy is important for migraine management, and provide specific tools to help patients improve their behavioral migraine management adherence.

- 2) The Headache Education version of the Status/Post app will include several education modules available in the app designed to increase general knowledge about migraine, including 1) diagnostic criteria of migraine and other common headaches, 2) pathophysiology of migraine, and 3) common comorbidities of migraine and other headaches.

6.1.2 METHOD OF ASSIGNMENT/RANDOMIZATION

A research assistant will randomize 60 people (n = 30 per group) to either the CDST Group or Headache Education Control Group, using block randomization with random size blocks using a computerized random number generator. Randomization will be stratified by gender. This research assistant will have no contact with any participant after he or she is randomized.

6.1.3 Selection Of Instruments/Outcome Measures

All measures were selected using materials from the National Institutes of Neurologic Disorders and Stroke (NINDS) Common Data Elements (CDE) initiative. When possible, measures from the National Institutes of Health Patient Reported Outcome Measurement System (PROMIS) were selected. Primary outcomes were selected based on previous studies evaluating adherence to migraine management (5, 20, 27, 54, 55).

Surveys

All surveys to be used have been uploaded via the iRIS website.

Demographics

NINDS CDEs will be used to evaluate: Age; Gender; Ethnicity; Race; Sexual Orientation; Education Level; Marital/Partner Status; Employment Status; Household and Income; Overall Health; Medical History; Height and Weight.

Migraine Symptoms

American Migraine Study/American Migraine Prevalence and Prevention (AMS/AMPP) Diagnostic Module.

The AMS/AMPP Diagnostic Module (34, 56) is a survey based on the ICHD-2 criteria for migraine; migraine criteria remain unchanged in the updated ICHD-3b (1). The sensitivity and specificity for migraine are 100% and 82% respectively (56).

Allodynia Symptom Checklist (ACS). The ACS is a 12-item survey designed to assess cutaneous allodynia in people with migraine (57). Items assess frequency of allodynia symptoms, with response options ranging from none to $\geq 50\%$ of the time. Scale development identified here factors: thermal, mechanical static, and mechanical dynamic. Initial development indicated good psychometric qualities (57).

Medications

Preventive. Preventive medication name, dose, frequency and timing of administration, route of administration, and start date will be evaluated using the NINDS CDE for medications taken on a regular basis.

Acute. Acute medication name, dose, frequency, route of administration, and start date will be evaluated using the NINDS CDE for medications taken on an as-needed basis.

Literacy

Newest Vital Sign. The Newest Vital Sign is a 6-item survey that measures health literacy (58). Participants respond to open-ended questions about a nutrition label, which are coded as correct or incorrect. It has demonstrated reliability and validity in primary care and electronic health settings (58, 59).

eHEALS. The eHEALS is an 8-item survey measure of eHealth literacy designed to evaluate knowledge, comfort, and participant self-evaluation of skills at finding, evaluating and applying electronic health information (60). The measure has demonstrated reliability and validity (60, 61).

Disability/Quality of Life

Migraine Specific Quality of Life Questionnaire (MSQL) v 2.1. The MSQL (37) is a commonly-used 14-item survey measuring quality of life in people with migraine. Items comprise three subscales (Role Restriction, Role Prevention, and Emotion Function) which have demonstrated adequate reliability and validity in a number of studies with migraine (37, 62).

Migraine Disability Assessment (MIDAS). The MIDAS (36, 63) is a commonly-used 5-item survey measuring disruption experienced due to migraine. Items target role functioning and ask about lost days of house-work, job-work, and non-work activities. Each item is an open question, allowing entry of number of days lost over 90 days). Total scores are categorized into four, graded levels of disability severity. Several studies have shown the test to have good internal consistency, reliability and construct validity (63, 64).

PROMIS Pain Interference – Short Form (PROMIS-PI). The PROMIS-PI (38) is an 8-item survey selected from a 41-item bank developed using Item Response Theory to evaluate the amount pain interfered

with daily activities and enjoyment of life in the past 7 days using a normative sample. Response options range from 1 (Not at all) to 5 (Very Much). The measure is commonly used to evaluate pain interference and has demonstrated reliability and validity in a number of studies (65).

Sleep

Pittsburgh Sleep Quality Index (PSQI). The PSQI (66) is a commonly-used, reliable and valid measure of sleep quality that includes 19 self-rated items and 5 items rated by one's bed partner; the first four self-rated items evaluate self-reported bed time, time to sleep onset, rise time, and hours of sleep per night, and are used in this study to evaluate sleep behavior.

Berlin Questionnaire (Berlin). The Berlin (67) is a 10-item survey evaluating risk factors for sleep apnea, including snoring (Category 1), waketime sleepiness and/or fatigue (Category 2), and the presence of obesity and hypertension (Category 3). Qualifying as "high risk" in two of the three categories is considered "high risk" for sleep apnea. Items within categories demonstrated good internal consistency, and adequate sensitivity and specificity across categories of sleep apnea severity (67).

PROMIS Sleep Disturbance – Short Form (PROMIS – SD). The PROMIS-SD is an 8-item survey (43) selected from a 27-item bank (68) developed using Item Response Theory to evaluate sleep disturbance using a normative sample. The first item assesses perceived sleep quality, with response options on a 5-point Likert scale ranging from very poor to very good; the remainder of the items evaluate the extent to which participants endorse problems with sleep, with response options on a 5-point Likert scale ranging from not at all to very much. It has demonstrated validity related to other measures of sleep disturbance, including actigraphy (43, 68).

Stress

Perceived Stress Scale (PSS). The PSS (41, 69) is a 10-item survey evaluating frequency of perceptions of stress (feeling life is unpredictable, uncontrollable, or overloaded) in the past month, with response options on a 5-point Likert scale ranging from never to very often. The PSS is the most commonly used survey of stress, has normative data from the United States, and has demonstrated reliability and validity for a two-factor model in numerous patient samples (70, 71).

Daily Stress Inventory (DSI). The DSI (42) is a 53-item survey evaluating whether 53 common daily hassles (e.g., performed poorly at task, ignored by others) occurred (Response options: Yes/No), and the extent to which hassles that occurred were appraised as stressors, with response options on a 7-point Likert Type scale ranging from "occurred but was not stressful" to "caused me to panic." The scale has demonstrated concurrent and construct validity (42), and has been associated with headache onset in people with chronic migraine and chronic tension-type headache (15).

Psychiatric Symptoms

PROMIS Depression Short-Form (PROMIS-D). The PROMIS-D (39) is an 8-item survey selected from a 28-item bank assessing severity of depression symptoms in a normative sample. Items assess frequency of depression symptoms ("I felt worthless") in the past 7 days with response options on a 5-point Likert scale ranging from "never" to "always." The PROMIS-D has demonstrated validity and increased utility in providing information about depression symptoms compared to other self-report measures (39, 40, 65).

PROMIS Anxiety Short-Form (PROMIS-A). The PROMIS-A (39) is an 8-item survey selected from a 29-item bank assessing severity of anxiety symptoms in a normative sample. Items assess frequency of anxiety symptoms ("I felt nervous") in the past 7 days with response options on a 5-point Likert scale ranging from "never" to "always." The PROMIS-D has demonstrated validity and increased utility in providing information about depression symptoms compared to other self-report measures (39, 40, 65).

Psychological Variables

Pain Catastrophizing Scale (PCS). The PCS (47) is a 13-item survey designed to assess the extent to which a participant utilizes maladaptive, catastrophic cognitive styles in response to painful experiences. Items comprise three subscales (Rumination, Magnification, and Helplessness) with response options on a 5-point Likert scale ranging from “not at all” to “all the time.” The current study utilizes the headache version, which has demonstrated reliability and validity in people with headache (48).

Headache Management Self-Efficacy (HMSE). The HMSE (44) is a 25-item survey designed to assess the extent to which a person with headache is confident in their ability to change their behavior to manage headache episodes. Response options are on a 7-point Likert scale ranging from “strongly disagree” to “strongly agree.” The HMSE has demonstrated excellent internal consistency and validity in samples with headache and migraine (44, 72).

Acute-Medication Self-Efficacy – Headache (AMSE-H). The AMSE-H (45) is a 7-item survey designed to assess the extent to which a person with headache is confident they can take his or her acute headache medication optimally. Response options are on an 8-point Likert scale and range from “strongly disagree” to “strongly agree.” The AMSE-H has demonstrated adequate internal consistency and construct validity (45).

Study-Specific Self-Efficacy. The study-specific self-efficacy survey includes three items that evaluate confident to adhere to each behavioral self-management strategy evaluated in this study (manage stress, sleep consistently, and eat and drink consistently), with response options on a 7-point Likert scale and range from “strongly disagree” to “strongly agree.” Items were developed using guidelines recommended by Bandura for self-efficacy scale development (46).

Outcome Expectancies. The study-specific outcome expectancies survey includes 7 items that evaluate the extent to which a participant believes that adhering to the specific migraine management strategies evaluated in this study will lead to a reduction in headache symptoms. Items were developed using guidelines recommended by Bandura (46) and items developed for other studies evaluating outcome expectancies for treatments for migraine and osteoporosis (45, 73).

Headache-Specific Locus of Control (HSLC). The HSLC (49) is a 33-item survey designed to assess the extent to which individuals with recurrent headache expect the occurrence, worsening, and improvement of their headaches are influenced primarily by their own behavior, by chance or fate, or by the actions of medical professionals. Items are coded on a 5-point Likert-type scale ranging from “strongly disagree” to “strongly agree.” It contains three subscales, which include Internal, Chance, and Medical Professionals. Each subscale demonstrated good internal consistency ($\alpha = 0.80-0.89$) and adequate 3-week test-retest reliability ($\rho = 0.72-0.78$). Subscales also demonstrated significant expected relationships with related measures (49).

Five Factor Mindfulness Questionnaire (FFMQ). The FFMQ (50) is a 39-item survey designed to evaluate the extent to which participants engage in mindfulness. Items comprise five subscales: Observing, Describing, Acting with Awareness, Non-Judging of Inner Experience, and Non-Reactivity to Inner Experience and are rated on a 5-point Likert scale ranging from “never or rarely true” to “very often or always true.” The FFMQ has demonstrated adequate internal consistency and construct validity (50).

Chronic Pain Acceptance Questionnaire (CPAQ). The CPAQ (51) is a 20-item survey designed to assess pain-related acceptance that was developed with patients suffering from chronic pain. Items comprise two subscales (Pain Willingness and Activity Engagement) and are rated on a 7-point Likert scale ranging from “never true” to “always true.” The current study uses the headache version. The CPAQ has demonstrated acceptable internal consistency ($\alpha = 0.78-0.82$) and construct validity in pain and migraine samples (51, 74).

Patient Satisfaction

Client Satisfaction Questionnaire (CSQ). The CSQ (52) is an 9-item survey designed to measure users' general satisfaction with human service programs. The CSQ is commonly used in treatment and program evaluation and has demonstrated excellent internal consistency (52).

Program Evaluation. The Program Evaluation survey is an 8-item, study-specific survey that evaluates the extent to which participants deemed the app to be effective (with response options on a 5-point Likert scale ranging from "not at all effective" to "very effective") and the extent to which participants are likely to recommend the app to a friend with migraine (with response options on a 5-point Likert scale ranging from "not at all likely" to "very likely"). Items were based on the program evaluation survey from a previous clinical trial evaluating preventive medication and behavioral migraine treatments (33).

Daily Diary

Morning. The morning diary will include measures assessing a) **Menstruation**, b) **Headache Symptoms** using ICHD-3b migraine criteria (1), c) **Acute Medication Usage** with items used in other headache medication adherence studies (54), and d) **Sleep Behavior**, using selected items from the Consensus Sleep Diary (75).

[figure not shown]
Afternoon. The afternoon diary will include measures assessing a) **Headache Symptoms** using ICHD-3b migraine criteria (1), and b) **Acute Medication Usage** with items used in other headache medication adherence studies (54).

Evening. The evening diary will include measures assessing a) **Preventive Medication Usage** with an item used in other headache medication adherence studies (54), b) **Headache Symptoms** using ICHD-3b migraine criteria (1), c) **Acute Medication Usage** with items used in other headache medication adherence studies (54), d) **Eating and Hydration Behavior** using one item asking participants to check off each hour during which they consumed food in the past 24 hours, and one item asking participants how many glasses of liquids they consumed in the past 24 hours, e) **Stress Level and Management** using a 0-10 Visual Analog Scale to rate stress level and a single item assessing stress management, and d) **Migraine Disability** using an abbreviated daily version of the MIDAS (36).

6.1.4 Intervention Administration

During Phase 1, the CDST or Headache Education version of the app will be administered to participants for one week. During Phase 3, the CDST or Headache Education version of the app will be administered to participants for 3 months. In both Phases, participants will download the app to their personal Apple device, or to a study-provided Apple device. Participants will receive a series of education modules (Figure 6.1.4), and for participants in the CDST group, notifications in the app tailored based on diary entries, which occur three times daily.

Figure 6.1.4

Treatment fidelity is conceptualized as the app providing the education and reminders at the allocated times. The app will monitor this information internally during both Phase 1 and 3.

6.1.4 Reaction Management

The expected risk of the CDST intervention is increased headache activity due to inhibition of therapeutic choice of participants. This risk is considered minimal. Participants may reach out to the research coordinator at any time if they experience discomfort or distress related to the study. The research coordinator will proactively assess participant reactions to the study in bi-weekly check-ins. The unblinded research assistant will also monitor participant's headache diary recordings to evaluate reactions to the study. Participants who report, or are suspected to have, clinically significant discomfort or distress during the study will immediately be reported to the PI, [name], Ph.D., clinical psychologist. [name] will assess the reaction and determine whether further action is warranted, such as an intervention plan or referral for treatment. If [name] is unavailable, or if her role as PI would interfere with her ability to assess and intervene with participant distress, [name], Ph.D., clinical psychology and Director of Clinical Training at Ferkauf Graduate School of Psychology, Yeshiva University ([contact]) will assess and determine the best course of action in the case of participant distress.

6.2 Assessments

6.2.1 Efficacy

The primary outcome variables will be **adherence to acute and preventive migraine management strategies**. All primary outcome variables will be assessed through the daily electronic headache diary, collected through the Status/Post app and captured by the REDCap system.

Adherence to Acute Migraine Management Strategies.

	When assessed	Question asked	Indication of adherence	Indication of non-adherence
Stress	each evening	whether they used a stress management strategy today	Yes	No
Sleep	each morning	when they got in and rose out of bed	Within one hour of median	Outside of one hour of median
Eating	each evening	whether they ate at least three times that day	Yes	No

Treat Early: When participants record headache activity, they will record type, timing, and current pain level for each acute medication dose taken. Treating early is operationalized as taking acute medication while the pain is mild.

Avoid Overuse: Avoiding overuse is operationalized as taking fewer than 10 triptans and 15 NSAIDS/acetaminophen per month.

Adherence to Preventive Migraine Management Strategies:

Adherence to Preventive Behavioral Strategies: Each participant will record information related to a single strategy: stress management, sleep management, or consistent eating. Participants will record either 1) whether they used a stress management strategy today (assessed each evening; Yes = adherent, No = non-adherent), or 2) when they got in and rose out of bed (consistent bedtime and rise-time; assessed each morning; Within 1 hour of median = Adherent, outside of 1 hr of median = Non-Adherent), or 3) whether they ate at least three times that day (consistent eating, assessed each evening; Yes = Adherent, No = Non-adherent).

Adherence to Preventive Medication: If a participant is taking a preventive medication, they will record whether they took preventive medication each day. Taking preventive medication = Adherent, Not taking preventive medication = Not-adherent.

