5.2 OUTCOME VARIABLES

5.2.1 PRIMARY OUTCOME VARIABLES

The primary outcome variables will be **adherence to acute and preventive migraine management strategies**. All primary outcome variables will be assessed through an electronic headache diary.

Adherence to Acute Migraine Management Strategies.

- a) **Treat Early:** When participants record headache activity, they will record type, timing, and current pain level for each acute medication dose taken. Treating early is operationalized as taking acute medication while the pain is mild.
- b) **Avoid Overuse:** Avoiding overuse is operationalized as taking fewer than 10 triptans and 15 non-specific pain medications (NSAIDs and acetaminophen) per month.

Adherence to Preventive Migraine Management Strategies:

- a) **Adherence to Preventive Behavioral Strategies:** Each participant will record information related to a single strategy: stress management, sleep management, or consistent eating. Participants will record either 1) whether they used a stress management strategy today (assessed each evening; Yes = adherent, No = non-adherent), or 2) when they got in and rose out of bed (consistent bedtime and rise-time; assessed each morning; Within 1 hour of median = Adherent, outside of 1 hr of median = Non-adherent).

Adherent), or 3) whether they ate at least three times that day (consistent eating, assessed each evening; Yes = Adherent, No = Non-adherent).

b) **Adherence to Preventive Medication:** If a participant is taking a preventive medication, they will record whether they took preventive medication each day. Taking preventive medication = Adherent, Not taking preventive medication = Not-adherent.

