5.2.2 SECONDARY OUTCOME VARIABLES

Migraine Symptoms

- a) **Headache days** per 30 days as assessed by daily headache diary.
- b) **Average head pain severity** as assessed by daily headache diary.

Distress and Disability

- a) **Migraine-Related Disability** as assessed by the Migraine Disability Assessment (MIDAS) (36).
- b) **Migraine-Specific Quality of Life** as assessed by the Migraine-Specific Quality of Life Questionnaire (37).
- c) **Pain Interference** as assessed by the PROMIS-Pain Interference (38).
- d) **Depression symptoms** as assessed by the PROMIS-Depression Short Form (39, 40).
- e) **Anxious symptoms** as assessed by the PROMIS-Anxiety Short Form (39, 40).

Psychological Factors

- a) **Stress** as assessed by:
 - a. The Perceived Stress Scale (41).
 - b. The Daily Stress Inventory (42).
 - c. Daily ratings of perceived stress on a 0-10 numeric rating scale.
- b) **Sleep** as assessed by:
 - a. The PROMIS Sleep Disturbance (43).
 - b. A daily rating of sleep quality on a 5-point Likert-type scale ranging from “Very Poor” to “Very Good.”
 - c. A daily rating of sleep hours.
- c) **Headache Management Self-Efficacy** as assessed by the Headache Management Self-Efficacy (HMSE) scale (44)
- d) **Acute Medication Self-Efficacy** as assessed with the Acute Medication Self-Efficacy – Headache (AMSE-H) (45)
- e) **Study-Specific Self-Efficacy** as assessed by items based on the HMSE and AMSE-H, assessing self-efficacy for study-specific lifestyle and preventive medication adherence.
- f) **Outcome Expectancies** as assessed by items based on items used in other studies (46) to assess each preventive and acute migraine management strategy.
- g) **Catastrophizing** as assessed by the Pain Catastrophizing Scale (47, 48).
- h) **Locus of Control** as assessed by the Headache-Specific Locus of Control Scale (49).
- i) **Mindfulness** as assessed by the Five Factor Mindfulness Questionnaire (50).
- j) **Acceptance** as assessed by the Chronic Pain Acceptance Questionnaire (51).

Feasibility and Acceptability

- a) **Patient Satisfaction** as assessed by the Client Satisfaction Questionnaire (52).
- b) Perceived effectiveness of intervention as assessed by the **Program Evaluation** Survey (based on the program evaluation survey used in the Treatment of Severe Migraine Trial (33)).
- c) **Adverse Events** as assessed by the adverse events check-ins.
- d) **Adherence Rates** to the diary as assessed by proportion of entries completed.

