6.4 Statistical Method

6.4.1 Statistical Design

Basic descriptive statistics (e.g., means, standard deviations, frequencies) for variables of interest will be computed. Graphical approaches will be used to further explore the data where appropriate. The outcomes are either 1) repeated measures of binary adherence to each migraine management strategy [coded each day as 0 (did not adhere) or 1 (adhered)] or total number of non-adherence days for each migraine management strategy over the relevant time-frame. Longitudinal binary outcomes will be analyzed using randomized logistic models, and number of total non-adherence days will be examined using Poisson regression models. SAS 9.3 will be used in the analyses. All tests are two-sided using significance level 0.05.

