6.4.3 Planned Analyses

6.4.3.1 Primary Analyses

Primary Objective: Describe and analyze how individual differences and conditions influence adherence to preventive and acute migraine management strategies.

Phase 2 diary data will be utilized. Random effects logistic models will be used to examine the effects of individual differences (e.g., age and gender) and circumstances (headache days/last 7 days, variations in stress) on daily adherence to migraine management strategies during the initial three-month study period. The random effects logistic model is a kind of generalized linear mixed effects model which can take account of missing data due to drop outs. This type of analysis yields robust estimates even in situations when observations are missing both at random, and not at random. The total number of non-adherence days at the end of follow-up will also be obtained, and the effect of individual characteristics and conditions on the rate of non-adherence will be examined using Poisson regression model with log of length of follow-up as offset.

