6.4.3.2 Secondary Objectives Analyses

Secondary Objective: Develop a tailored CDST to improve preventive and acute migraine management strategies.

Phase 3 diary data will be utilized. As described above, random effects logistic models will be used to examine the effects of Group (CDST vs. Headache Education Control), Time, and Group X Time on daily adherence to migraine management strategies. Poisson regression model with log of length of follow-up as offset will be used to examine differences between the groups on total number of nonadherence days at the end of the study.

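### Avoid Overuse, a primary outcome, is defined per month, but the plan analyses daily adherence and non-adherence days, with no rule linking the two

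*Combined protocol and SAP*

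**What the plan says.** Section 5.2.1 lists Avoid Overuse as the second acute strategy among the primary outcome variables and defines it as "taking fewer than 10 triptans and 15 non-specific pain medications (NSAIDs and acetaminophen) per month". Section 6.2.1 (Efficacy) repeats this: "Avoiding overuse is operationalized as taking fewer than 10 triptans and 15 NSAIDS/acetaminophen per month". Both give a monthly total and nothing finer. The window is not defined. By contrast, Section 5.2.2 counts headache days "per 30 days as assessed by daily headache diary".

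Section 6.4.1 gives two forms for the outcomes. One is "repeated measures of binary adherence to each migraine management strategy [coded each day as 0 (did not adhere) or 1 (adhered"; the other is a count of non-adherence days for each strategy. The planned models follow these forms:

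- Section 6.4.3.1 (Phase 2) models effects "on daily adherence to migraine management strategies during the initial three-month study period" by random effects logistic regression. It adds that the "total number of non-adherence days at the end of follow-up will also be obtained", for a Poisson regression with log follow-up as offset.
- Section 6.4.3.2 (Phase 3) models Group, "Time, and Group X Time on daily adherence to migraine management strategies", and uses Poisson regression for "differences between the groups on total number of nonadherence days at the end of the study".

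Neither section makes an exception for Avoid Overuse.

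**The concern.** A person either stays under a monthly limit or does not. That result has no value on a given day until someone supplies a rule. Several rules are possible: copy the month's result to all its days, count days as adherent until the limit is reached, or use a trailing 30-day total. They give different data from the same diary, and some break the assumptions of the planned models. The analyst would have to choose after seeing the diaries, for an outcome the protocol calls primary.

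Two other parts of the protocol depend on the same missing rule. Phase 3 entry (Synopsis and Section 5.3.2) requires under 50% adherence to at least one acute strategy. There are only two acute strategies, and percent adherence to a monthly limit is not defined. The odds ratios in Section 6.4.2 rest on repeated daily measurements and are not shown to apply here.

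**Working it through.** **1. Is there a bridge in the text?** The nearest wording is in Section 6.4.1, which ties the count of non-adherence days to the applicable period. It limits the period of counting but does not say when a day is non-adherent for overuse. Section 6.4 names no daily coding, monthly model, window or rule for incomplete months. The text between Sections 5.1.1 and 5.2 was not available to check, but the statistical sections do not refer to a conversion given there.

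**2. The plan's own figure.** Section 6.4.2 gives a detectable odds ratio of 1.28 with 30 per group and 80% power. I used exp[(1.96 + 0.84) × SE], with SE² = 2 / [30 × p(1 − p) × m]. Here p = 0.37 (the stress-management proportion), and m is the effective number of daily values per person over 90 days after the stated drop-out.

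| Correlation assumed | m | Detectable odds ratio |
|---|---|---|
| Independent days | 79.3 | 1.18 |
| Autoregressive, 0.6 | 20.3 | 1.39 |
| Exchangeable, 0.6 | 1.64 | 3.22 |

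None gives 1.28. The correlation structure and the Phase 3 adherence rate are not stated, so the figure can be neither confirmed nor called wrong. Its basis is daily data, and no rate or correlation is given for Avoid Overuse.

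**3. Same diary, different rules.** Take two triptan doses on days 4, 8, 12, 16 and 20 of each of three 30-day months, 10 per month.

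- By month: 10 is not fewer than 10, so 0 of 3 months are adherent. Copied to days, that is 90 non-adherence days.
- Adherent until the limit is reached: days 1 to 19 of each month, 3 × 19 = 57 of 90 days, so 33 non-adherence days.
- Trailing 30-day total below 10: days 1 to 19 of the first month only, 19 of 90 days, so 71 non-adherence days.

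Against the 50% entry criterion these are 0%, 63% and 21%, so the rule can decide which side of the line a person falls on. This diary has 10 medications on only 5 days. Section 2.1 states overuse in days per month, while Sections 5.2.1 and 6.2.1 count medications, so the unit also needs reconciling.

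**4. Copying the monthly result to days: logistic model.** Assumptions: 30 per group, three months, no group or time effect, and months independent given the person. Monthly adherence is 0.5 or 0.7, and the random-intercept SD is 1 or 2 on the logit scale. The model is a random-intercept logistic with Group, Time (month) and Group X Time, two-sided 0.05, 400 simulated trials per setting. Rejection rates under the null:

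| Adherence, SD | Group X Time, copied | Group X Time, person-month | Group, copied |
|---|---|---|---|
| 0.5, 1 | 80.5% | 6.2% | 6.2% |
| 0.5, 2 | 75.2% | 5.0% | 6.8% |
| 0.7, 1 | 75.2% | 4.5% | 6.0% |
| 0.7, 2 | 77.0% | 5.0% | 9.2% |

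Smaller repeat runs of the first setting (100 and 120 trials) gave 73% and 74%. A rough check agrees: each value is repeated 30 times, so standard errors for within-person contrasts shrink by about √30 = 5.48. The false-positive rate is then about 2[1 − Φ(1.96/5.48)] = 72%.

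**5. Copying: Poisson day count.** The count is 30 × (non-adherent months out of 3). With independent months and a proportion q non-adherent, the mean is 90q and the variance is 900 × 3q(1 − q), so variance/mean = 30(1 − q). False positives are 2[1 − Φ(1.96/√ratio)].

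| q (assumed) | Variance/mean | SE too small by | False positives |
|---|---|---|---|
| 0.1 | 27 | 5.20 | 70.6% |
| 0.3 | 21 | 4.58 | 66.9% |
| 0.5 | 15 | 3.87 | 61.3% |

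**The case against.** The strongest reply is that the plan never says to copy monthly results to days, so the error rates in steps 4 and 5 belong to a procedure nobody has proposed. That stands. The rates are conditional on copying, on a random intercept with month as Time, and on assumed adherence rates. A reader might infer that this trial has a 75% to 81% false-positive rate. The documents do not support that, because they specify no conversion at all. Even under copying, the Group main effect stays near nominal, and no error rate was computed for the Phase 2 analysis.

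A second reply is that Section 6.4.1 assigns longitudinal binary outcomes to the logistic model, and a yes/no value per person-month is one. That is correct, so it would be too strong to say that neither planned model fits. The conflict lies in the daily coding and the Poisson day count.

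Third, it is tempting to claim a specific loss of power. With independent values and no drop-out, a simple calculation gives a detectable odds ratio of 1.17 for 90 daily values and 2.35 for three monthly ones. At a correlation of 0.6, the limit that Section 6.4.2 allows, the same method gives 3.24 and 3.70, so most of the gap closes. No replacement odds ratio is justified.

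Fourth, the entry criterion changes hands only for some people. They must be under 50% on a preventive behavioral strategy, not already under 50% on Treat Early, and not excluded for medication overuse headache. The documents do not show how many that is, nor do they favour one scoring rule for entry.

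**Conclusion.** The concern holds as a mismatch between the outcome's definition and its analysis. A primary outcome is defined only by the month, the plan analyses every strategy by day, and no stated rule connects them. The daily coding and the non-adherence-day Poisson count do not suit this outcome; the random effects logistic model does, once the unit is the person-month.

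The size depends on the rule chosen. One diary gives 0%, 63% or 21% adherence under three rules. If months were copied to days, null rejection would be about 75% to 81% for Group X Time and about 60% to 70% for the Poisson count, against about 5% for Group X Time by person-month. These rates rest on the assumptions in steps 4 and 5. The Phase 3 entry percentage shares the gap, with an unknown number of people affected, and the Section 6.4.2 odds ratios are not shown to cover this outcome. The point is worth correcting, but it concerns one outcome among several. The simulated effects concern Phase 3, a 60-person pilot for the secondary objective.

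**What to change.** - Take Avoid Overuse out of the daily logistic model and the non-adherence-day Poisson count. Analyse it as one binary value per person-month with the random effects logistic model or GEE, or as a monthly medication count with allowance for overdispersion.
- Define the month window and the scoring of incomplete months before analysis.
- If a daily version is kept, pre-specify its derivation, do not copy the monthly value to days, and allow for serial dependence.
- State one scoring rule for the under-50% entry criterion, and document the rule used for anyone already entered. Section 5.1.1 schedules recruitment from 2018 and this version is dated June 2021, but current enrolment is not stated.
- State that the Section 6.4.2 odds ratios do not cover this outcome.
- Reconcile the unit: medications in Sections 5.2.1 and 6.2.1, days in Section 2.1. The threshold itself is for the sponsor.

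The cost is small. The diary already records the type and timing of each acute dose, so no new data are needed. The price is some SAP wording, fewer observations and a less precise estimate for this one outcome.
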